- The study design would implement a randomized non-blinded clinical trial. Randomization will be performed by having sealed envelopes at the time of enrollment with either "original" or "VSP" written on cards.
- Both groups of patients will be treated by a team of oral and maxillofacial surgery residents and attending surgeons.
- The patients will be divided into two groups, the treatment group and control group. Records for both groups will be evaluated by the investigators and the patients will be asked to follow up in the OMFS Clinic at Memorial Hermann and treated by the Oral & Maxillofacial Surgery service.
 - The treatment group corresponds to patients undergoing mandibular reconstruction via open reduction internal fixation (intraoral or extraoral approach) utilizing virtual surgical planning via 3D Systems, bite registration and fabrication of occlusal splint via intraoral digital scanner, and mandibular hardware
 - The control group will include patients that undergo mandibular reconstruction via open reduction internal fixation (intraoral or extraoral approach) in standard fashion (without virtual surgical planning assistance and occlusal splint)

Study Population

Our study population consists of all patients with complex mandible fractures presenting to the University of Texas Health Science Center at Houston, Department of Oral & Maxillofacial Surgery facility at Memorial Hermann Hospital between October 2019 and October 2021 (until adequate data is obtained for significant statistical analysis).

- We anticipate recruitment of approximately 50 patients (25 patients for each control and treatment group) from Memorial Hermann Hospital. The control group will undergo mandibular fixation via standard open reduction internal fixation techniques. The VSP group will undergo mandibular fixation with standard open reduction internal fixation techniques and utilization of intraoperative occlusal splint, Virtual Surgical Planning via 3D Systems, and Stryker Anatomical Models.
- Inclusion criteria:
 - Patient consent
 - Male or female; 18 years or older
 - Complex mandible fracture (at least two fractures) that require ORIF of at least one fracture.
- Exclusion criteria:
 - Patient refusal to participate in study
 - Infected mandible fracture
 - Closed reduction treatment of mandible fracture
 - Fractures older than 2-3 weeks at the time of treatment
 -

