 - Other etiologies than trauma of the mandibular fracture or pathologic fracture secondary to benign or malignant pathology that may require resection
 - Pregnant patients will NOT be excluded from the study
 - Co-morbidities (auto-immune disease, osteoporosis, titanium or metal allergy, uncontrolled diabetes (A1c greater than 8)

Patient would be enrolled upon evaluation and consent for mandibular reconstruction at the University of Texas Health Science Center at Houston, Department of Oral & Maxillofacial Surgery treatment facility at Memorial Hermann Hospital - Texas Medical Center

Study Procedures

- No additional time will be required from participants than the time required for the normal care, treatments, or management. Patients will not be charged anything additional to participate in the study and will also not receive any compensation.
- Patients will have post-operative CT scan to ensure adequate reduction and fixation of fractures
- Patients will be re-evaluated at 3 follow up visits within 6 weeks to determine mandible fracture healing.
 - Post-op (prior to discharge), 1 week, 3 weeks +/- 1 week, 6 weeks +/- 1 week
- Collected data will include:
 - Age, gender, operating time (ORIF time, total operating time), fracture pattern
 - ORIF time will be defined as starting after the dissection is complete and fractures are reduced until final screws are placed.
 - Ideally the dissection, reduction, closure should not change from the control to the treatment
 - Accuracy of fracture reduction
 - Type of archbars, fit of guides, type of approach
 - Surgical revisions, infections, mouth opening
 - Hardware failure defined as plate fracture or screw loosening
- Once data is collected, variability will be calculated within individual test results.

Data & Safety Monitoring

- Adverse events
 - Expected adverse events: pain, infection, bleeding, swelling, trismus, possible nerve damage, damage to adjacent structures
 - Unexpected adverse events: repeat fractures, trauma post-surgery, plate fractures, loose screws, mal-unions, non-unions, poor cosmetic outcome, delayed healing
 - Potential serious adverse events: sepsis from infection, osteomyelitis
- Unanticipated problems will be discussed amongst investigators.
- Methods of measuring results will be discussed amongst investigators and standardized so that measurements remain consistent from investigator to investigator.

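### The primary endpoint depends on how many fractures are plated, but the protocol does not require that number to be planned on paper before allocation, does not list it among the data, and does not adjust for it.

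*Combined protocol and SAP*

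**What the plan says.** - **Eligibility** (Study Population, inclusion criteria): "Complex mandible fracture (at least two fractures) that require ORIF of at least one fracture". The number of fractures plated can run from one to all of them.
- **Primary endpoint** (Study Procedures; also the Objectives table): "ORIF time will be defined as starting after the dissection is complete and fractures are reduced until final screws are placed". It is one interval per patient, not a time per site or per plate.
- **Allocation** (Study Design): "The study design would implement a randomized non-blinded clinical trial", and "Randomization will be performed by having sealed envelopes at the time of enrollment". Enrollment takes place on evaluation and consent. No section asks for the planned fixation to be written down first.
- **Equal surgery between arms** (Study Procedures and Objectives): "Ideally the dissection, reduction, closure should not change from the control to the treatment". This is an aspiration, and it does not mention fixation, the part that the clock measures.
- **Data collected** (Study Procedures): "Age, gender, operating time (ORIF time, total operating time), fracture pattern", then accuracy of reduction, arch bars, fit of guides, approach and complications. The list has no count of sites or plates.
- **Analysis** (Statistics): a generalized linear model compares the groups. No covariate, family or link is named.

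**The concern.** Fracture pattern describes the injury, not the operation. Under the inclusion rule, the same pattern may be plated at one site or at two. Two patients with identical injuries and equally quick plating can therefore have very different ORIF times.

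This matters in two ways. First, the number of sites adds variation between patients that has nothing to do with VSP. It can also fall unevenly between two arms of 25 by chance. Second, the surgeon knows the arm, and one arm has an extra planning step. The number of sites plated could therefore come to differ by arm, in either direction. A difference in ORIF time could then reflect plating speed, the amount plated, or both, and the listed data would not directly show which.

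**Working it through.** **1. The plan's own figure.** Inputs from the Statistics section: f = 0.4, 25 per group, power 0.8, alpha 0.05. For two equal groups d = 2f = 0.8. The exact noncentral t calculation has df = 48 and noncentrality 0.8 × √(25/2) = 2.83, and gives power 0.791. The exact requirement is 26 per group and the normal approximation gives 25. The stated size reproduces, with no margin.

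**2. Assumptions.** The documents give no SD of ORIF time, no time per site and no distribution of sites. For illustration, each patient has one or two sites plated. A second site adds m SDs, with m from 0.5 to 2, where SD means the spread among patients with the same number of sites.

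**3. Cost in precision when the arms are balanced.** Suppose half the patients have a second site, and the planned number closely predicts the actual number.
- Total variance = 1 + m² × 0.5 × 0.5 = 1 + m²/4.
- Share of variance due to sites = (m²/4) / (1 + m²/4).
- The design effect d = 0.8 is on the total SD. Adjusted d = 0.8 × √(1 + m²/4), with df = 47.

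| m | Variance due to sites | Adjusted d | Power, unadjusted | Power, adjusted |
|---|---|---|---|---|
| 0.5 | 0.0625/1.0625 = 6% | 0.82 | 0.79 | 0.81 |
| 1 | 0.25/1.25 = 20% | 0.89 | 0.79 | 0.87 |
| 2 | 1/2 = 50% | 1.13 | 0.79 | 0.97 |

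**4. Chance imbalance.** Take two independent binomial counts with n = 25 and probability 0.5. They differ by 5 patients or more (20 points) in about 20% of trials. This does not raise the false-positive rate: with equal underlying shares, simulated rejection stays at about 5%. It does make the single observed comparison harder to read.

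**5. Arm-dependent imbalance with no true VSP effect.** Let p₁ and p₂ be the shares plated at two sites in the two arms.
- Spurious d = m(p₁ − p₂) / √(1 + m²[p₁(1 − p₁) + p₂(1 − p₂)]/2).
- Example: m = 2, 60% against 40%. The numerator is 2 × 0.20 = 0.40. The denominator is √(1 + 4 × 0.48/2) = 1.40. The result is d = 0.29.

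Rejection rates come from two-sided t-tests on 40,000 simulated trials per setting, 25 per arm.

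| Shares at two sites | Spurious d, m = 0.5 to 2 | As share of d = 0.8 | Rejection rate |
|---|---|---|---|
| 55% vs 45% | 0.05 to 0.14 | 6% to 18% | 5% to 8% |
| 60% vs 40% | 0.10 to 0.29 | 12% to 36% | 6% to 17% |
| 65% vs 35% | 0.15 to 0.43 | 18% to 54% | 8% to 33% |

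Small imbalances do little harm. The bias is material only when both the imbalance and the time per site are large.

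**The case against.** A reader might infer that extent is decided after the card is seen, that it will differ by arm, and that nobody could tell. The documents do not support this.

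- **A plan may already exist.** Eligibility requires a judgment that ORIF is needed, closed reduction is an exclusion, and Study Design has patients recruited once assessed and scheduled. The protocol is silent on recording the plan, which is not the same as leaving it open. This stands.
- **There is no evidence of arm-dependent surgery.** The Ethics section says that the study will not affect treatment. That is a statement of intent, not a control, but nothing in the documents points the other way. This stands.
- **The count is recoverable.** Every patient has a post-operative CT, and records are reviewed in both arms, so plated sites could be counted later. Data Handling & Record Keeping refers to attached data sheets that are not in the available text, so the gap can be asserted only for the Study Procedures list. This stands, but a later count cannot reliably show what was planned before allocation.
- **Approach is a different matter.** One might add the choice of an intraoral or extraoral approach. Approach is a listed variable and can be compared by arm, and the clock starts after dissection and reduction. It is not part of this point.
- **Power already allows for the noise.** The design effect is standardized, so its SD includes variation in extent. This is true, and the required sample size does not change. Adjustment would still add power to a plan that has no margin.
- **A change in extent could be part of the effect of VSP.** If planning leads to fewer or more plates, that may belong to VSP as a strategy. This is fair, and it is a reason to report extent by arm and not to adjust for the actual number.

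**Conclusion.** The point holds as a cheap improvement to design and analysis. The primary endpoint depends on the number of sites plated. The protocol does not require the planned number to be recorded before allocation, the Study Procedures list omits the actual number, and the model does not use either.

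The size is unknown, because the documents give no times, SDs or site counts. If half the patients have a second site worth 0.5 to 2 SD, and the planned number closely predicts the actual number, adjustment raises power at the design effect from 0.79 to between 0.81 and 0.97. Under the same range for a second site and no true effect, a 20-point arm difference in two-site plating would give a spurious d of about 0.10 to 0.29. These figures show what could happen. They are not evidence that it does.

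**What to change.** 1. On the data sheet, before the envelope is opened, record the number of fractures planned for ORIF.
2. Name that number as a covariate in the ORIF-time model. It is fixed before allocation, so adjusting for it is safe.
3. After surgery, record the number of sites actually plated, and report planned against actual by arm as a check.
4. Do not adjust the primary comparison for the actual number, because it follows allocation and may be affected by it.

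The cost is one line before allocation, one count after surgery and one degree of freedom. The sample size, visits and treatment are unchanged, and no rule on which fractures to plate is implied. The limit should be stated: the covariate deals with noise and with chance imbalance in planned extent. An arm-dependent departure from the plan would be revealed by the planned-against-actual table, not removed.

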**Comparison of Operating Room Time Length with the Use of Virtual Surgical Planning Versus
Conventional Treatment of Mandible Fractures**

NCT04283981

Version Date: 02/10/2021

Protocol Title:	Comparison of Operating Room Time Length with the Use of Virtual Surgical Planning Versus Conventional Treatment of Mandible Fractures
Principal Investigator:	[name] [name]
UTHealth Co-Investigators:	[name] DDS MD FACS; [name] DDS MD PhD FACS; [name] DDS; [name] MD; [name] DDS; [name] DDS
Study Coordinators:	[name]; [name] APRN FNP; [name]
Population:	All patients presenting with diagnosed mandible fracture at Memorial Hermann Hospital
Number of Sites:	Memorial Hermann Hospital
Study Duration:	Between November 2019 and November 2021 (until adequate data is obtained for significant statistical analysis)
Subject Duration:	From the initial preoperative evaluation to end of treatment which is 2 months

General Information

Patients at Memorial Hermann Hospital who have an isolated mandibular fracture and who are appropriately consented will partake in this study. They will be split evenly into 2 groups which are virtual surgical planning (VSP) and the conventional surgery. The conventional surgery involves having medical grade CT in order to assess the mandible fracture and having an open reduction and internal fixation of the fracture. The reconstruction plate will be bent intra-operatively. VSP patients will also receive the medical grade CT and also receive intraoral scans for aid in assessing occlusion. 3D models of the patient's jaws will be made and set into the proper occlusion. A reconstruction plate will be bent before the surgery using these models to be used at the time of surgery. Advancements in VSP technology increasingly demonstrate improvements in operative efficiency and reduce operating time. Pre-surgical planning and fabricated guides can potentially improve intraoperative efficiency, postoperative outcomes, and minimize complications. Additionally, use of this technology may permit a reduction of operating costs associated with longer operating room and anesthesia times in conventional treatments. Another challenge presented with VSP is turn over time from the actual planning and fabrication of splints or anatomical models to having them ready for surgery. This can take between one to two weeks and delay treatment for acute trauma cases.

Objectives

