Excellent results have been shown for VSP on mandibular reconstruction with assistance from an intraoral scanner for modeling generated occlusal splints and pre-bent fixation plates. This randomized control study will attempt to determine whether there is reduction in operating time, costs, and post-operative complications. This treatment modality may potentially allow for increased accuracy, efficiency, and outcome in this surgical setting. A reduced time in the operating room could potentially lead to better outcomes for the patient while decreasing overall treatment cost. Hence, a decreased operating time, anesthesia time, and hospitalization could thereby, potentially, justify the additional preoperative costs that come with computer assisted surgical planning. Furthermore we will determine the effectiveness of remote 3D printing guides and models to decrease the turn over time of VSP.

Study Design

- In this randomized controlled study, we will evaluate patients from the University of Texas Health Science Center at Houston, Department of Oral & Maxillofacial Surgery treatment facility at Memorial Hermann Hospital

- from a patient population that undergoes mandibular trauma via open reduction internal fixation (ORIF) via intraoral or extraoral approach, using an intra-oral scanner, VSP® 3D Systems, and Stryker Anatomical Models.
- The study population will be composed of patients presenting with mandible fractures to Memorial Hermann Texas Medical Center in Houston, Texas from November 2019 to November 2021 (until adequate data is obtained for significant statistical analysis).
- Recruited and consented patients will be asked to attend the follow up appointments, for permission to review their records, to answer additional questionnaires, and have additional measurements/formal exam taken.
- Subjects will be re-evaluated at 3 within 6 weeks to assess the patient's mandible fracture healing via panorex or maxillofacial CT (follow ups: 1 week, 3 weeks +/- 1 week, 6 weeks +/- 1 week)
- Patients will be recruited from the Memorial Hermann Hospital when assessed and scheduled for mandibular reconstruction via open reduction internal fixation with VSP, fabrication of occlusal splint (from intraoral scanner), and 3D printed anatomical model for adaptation of pre-bent reconstruction plate.

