- The research team will periodically review its protocols to ensure maximal patient safety and data validity.

Statistics

- Generalized linear model will be used to identify data distribution differences between the two study groups.
- This data will be recorded using a standardized data sheet to be shared within the department.
- Power analysis was performed for an f-test, and to show a large effect size ($f=0.4$) between the groups will require:
 - $n = 25$ patients/group to achieve a power of 0.8 and a significant level of 0.05.
- **ANOVA-based power analysis figures require:**
 - $n = 26$ patients/group for a large effect size
 - $n = 64$ patients/group for a medium effect size
 - $n = 393$ patients/group for a small effect size

Ethics

- A written informed consent will be obtained from the adult subject. This site has submitted the consent documents for CPHS review.
- IRB approval will be sought from CPHS (Committee for the Protection of Human Subjects).
- Treatment and clinical management will not be affected by this study. The surgical procedure investigated in this study is considered standard of care.
- Informed consent for the review of records and permission to conduct additional questionnaires and measurements at each follow up appointment will be obtained from each patient prior to commencing the study.
- To protect the privacy of subjects, only members of the research staff including the attending doctors, residents, will have access to patient health information

Data Handling & Record Keeping

- Data collected electronically through the medical record system and recorded on the data sheets attached to this protocol. Access to source documents will be per respective EHR guidelines on computers that are encrypted, and password protected. The data sheets, including consents, will be kept with the principal investigator in a locked cabinet. The patients will also receive a copy of their consent forms. HIPAA compliance guidelines will always be used.
- Human subjects will not be directly identifiable, but only identifiable in the study database through identifying information (Hospital MRN)
- Age of patient will be recorded to replace birth date. Only specific disease information, sex, and age as potential identifier will be used. No identifiable patient name, number or birth date will be used in this study and subsequent publications.

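### The fracture-age exclusion uses a range as its limit and is dated to treatment, after the envelope; if applied that way, it can exclude a patient because of the card drawn

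*Combined protocol and SAP*

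**What the plan says.** The exclusion criteria under Study Population include "Fractures older than 2-3 weeks at the time of treatment". No single cut-off within that range is given.

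On the order of events, Study Design states "Randomization will be performed by having sealed envelopes at the time of enrollment" and describes the trial as unblinded. Study Population ends with "Patient would be enrolled upon evaluation and consent for mandibular reconstruction". Study Design also says "Patients will be recruited from the Memorial Hermann Hospital when assessed and scheduled for mandibular reconstruction", in a sentence that goes on to describe surgery with VSP.

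On waiting time, General Information names turnaround as a challenge of VSP: "This can take between one to two weeks and delay treatment for acute trauma cases". For the conventional arm the same section says "The reconstruction plate will be bent intra-operatively", and no planning wait is described. Objectives and Background Information add that the study will examine whether remote printing shortens the VSP turnaround. The documents give neither a turnaround for this trial nor a time to surgery for controls.

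Ethics says "Treatment and clinical management will not be affected by this study".

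**The concern.** An eligibility rule should depend only on facts that the allocation cannot change. This one refers to the age of the fracture on the day of surgery, and the plan itself says that one of the two treatments can postpone that day. If the rule is applied on that day, two patients with the same fracture at enrolment can have different fates: the one who drew VSP passes the limit while waiting and is excluded, and the one who drew conventional surgery stays in.

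The range makes this worse. Between two and three weeks there is a seven-day zone in which the plan gives no rule, and staff who know the card would decide.

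At stake is the comparability of the arms. Exclusions that depend on the card undo what randomisation provides. Recruitment is left open until enough data are in hand, so lost patients could be replaced; that would restore the number of patients but not the comparability.

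**Working it through.** The plan offers no calculation on this point. Its sample size is not in dispute here and is not used. The check is calendar arithmetic plus a reading of the sequence.

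**Inputs from the documents**
- Limit L: two to three weeks, so 14 or 21 days at its ends (Study Population).
- VSP turnaround T: one to two weeks, so 7 or 14 days (General Information). This is a general figure for VSP.
- Order: enrolment and envelope first, treatment later (Study Design, Study Population).

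**Not in the documents:** the turnaround in this trial, the control wait C, and the distribution of fracture age at presentation.

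**Step 1. Oldest fracture at the draw that still passes under VSP.** If surgery waits for the full turnaround, this is L − T.

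| Limit L | T = 7 days | T = 14 days |
|---|---|---|
| 14 days | 14 − 7 = 7 | 14 − 14 = 0 |
| 21 days | 21 − 7 = 14 | 21 − 14 = 7 |

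**Step 2. Fracture ages for which the card decides.** A control passes up to L − C, so the band runs from L − T to L − C and is T − C days wide, whichever limit is used.
- C = 0 (assumed): 7 − 0 = 7 or 14 − 0 = 14 days.
- C = 5 (assumed): 7 − 5 = 2 or 14 − 5 = 9 days.
- C = T: zero. The card decides nothing.

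**Step 3. One patient.** A fracture is 8 days old at the draw. VSP surgery falls between day 8 + 7 = 15 and day 8 + 14 = 22. That is over a 14-day limit at any stated turnaround, and over a 21-day limit only at the longest. Conventional surgery the next day (assumed) falls on day 8 + 1 = 9, inside both.

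**Step 4. Is there a safeguard?** At enrolment, age at surgery can only be projected. The recruitment sentence in Study Design refers to patients already assessed and scheduled, so a projection before the draw is possible. No text shown requires one, or says that the same wait is projected for both cards. No analysis population is defined, and nothing says how a randomised patient who passes the limit while waiting is handled.

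**Step 5. Can the bias be sized?** No. That would need the fracture-age distribution and both waits. In addition, Study Procedures starts the ORIF clock once the fractures are reduced, so any extra difficulty in reducing an older fracture falls outside the primary endpoint. Total operating time, accuracy of reduction, infections and revisions are also collected, and that start point does not protect them.

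**The case against.** The strongest reply is that the criterion stands in an ordinary eligibility list and would naturally be judged at assessment, from the expected surgery date, before any envelope is opened. The neighbouring exclusion of closed-reduction cases also refers to later treatment and is plainly judged from the plan made at assessment. This reading is open, and it makes the harm conditional. It does not remove the defect: the text dates the criterion to treatment, and a projection made before the draw is fair only if it is the same for both arms.

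The record is also incomplete. The data sheets attached to the protocol are not shown and might hold an eligibility check, and an empty bullet follows the criterion. The finding is therefore limited to the text shown.

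A reader might infer that the plan provides for removing patients after randomisation. It does not; no section describes such a removal. A reader might also take one to two weeks as the wait in this trial. The figure is a general one, and shortening it by remote printing is one of the trial's own questions.

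Finally, Study Procedures says "No additional time will be required from participants than the time required for the normal care, treatments, or management". It is tempting to call this a contradiction of the stated delay, but the sentence stands beside charges and compensation and can be read as the time asked of participants. The point does not rest on it. The tension with the Ethics statement is real, though it would exist without the fracture-age rule.

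**Conclusion.** The concern holds as a defect of wording and timing, and should be fixed. The limit is a range, and the criterion refers to a moment after an unblinded draw. The plan also says that one arm's technique can delay that moment. Confidence is high on this.

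The consequence is conditional: the rule must be applied after the draw, and VSP patients must wait longer than controls. Under the stated turnaround, the entry window for VSP shrinks to 7 or 0 days with a 14-day limit and to 14 or 7 days with a 21-day limit. With equal waits the arms do not differ.

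A reader might infer that the comparison of ORIF time is biased, perhaps in favour of VSP. The documents do not support that. Neither the size nor the direction of a bias can be computed, no section links fracture age to the time from reduction to the final screw, and the definition of ORIF time may limit any effect on the primary endpoint.

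**What to change.** - **Eligibility.** State that fracture age, like every eligibility criterion, is assessed once, before the envelope is opened, against a single limit. The investigators set that limit by reconciling the two-to-three-week range with the turnaround in General Information. If the limit refers to the surgery date, project that date before the draw in the same way for both arms.
- **Follow-up and analysis only.** Drop no randomised patient because of fracture age after the draw, and analyse patients in the arm on the card. How a patient past the limit is treated is left to the investigators.
- **Reporting.** Give by arm the time from injury to surgery, and the randomised patients with no ORIF time and the reason. Record the injury date if the data sheets do not already hold it.
- **Consistency.** Reconcile the delay described in General Information with the Ethics statement that clinical management is unaffected.

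The cost is protocol wording, at most one data field and two lines in the report. The main downside is recruitment: a common projected wait may screen some patients out of both arms. With the stated turnaround as that wait, the windows in Step 1 would apply to everyone; at a 14-day limit and a 14-day wait, only fractures on the day of injury would qualify. Patients without an ORIF time would still be missing from the primary analysis; the report by arm shows this but does not cure it.

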Objective of this randomized controlled study is to compare operating room time between conventional treatment techniques (without VSP) versus use of VSP and surgically-guided techniques. Surgically-guided techniques will include use of an occlusal splint (from digital intraoral scanner), and a 3D printed anatomical model for adaptation of pre-bent titanium plates. Additionally we will determine if remotely printing anatomical guides and splints is feasible and can decrease turn over time for VSP.

OBJECTIVES	ENDPOINTS	JUSTIFICATION FOR ENDPOINTS
Primary		
To compare OR time between conventional treatment techniques (without VSP) vs use of VSP and surgically guided techniques	ORIF time, which is defined as starting after the dissection is complete and fractures are reduced until final screws are placed. Ideally the dissection, reduction, closure	To compare whether or not the intervention (VSP) yielded decrease OR time

OBJECTIVES	ENDPOINTS	JUSTIFICATION FOR ENDPOINTS
	should not change from the control to the treatment	
Secondary		
To compare and contrast the effect of any other variables that might have an effect on the overall result	Age, gender, fracture pattern, Type of archbars, fit guides, type of approach, Surgical revisions, infections, mouth opening, Hardware failure defined as plate fracture or screw loosening	Age, gender, and fracture pattern is basic data needed to analyze results. The rest of the endpoints are important because they might possibly have an effect on the primary objective.

Background Information

Mandibular fractures are the second most common facial bone fracture [1] due to its prominent position in the maxillofacial region and the mandible's relative lack of structural support. The most common cause of injury is low impact blunt trauma, including motor vehicle accidents (MVCs), physical assault, and sports injuries [1, 2]. Advancement in mandibular reconstruction increasingly allow for interventions that result in reduction of facial deformities [3]. With the application of virtual surgical planning (VSP), the planning process has become more precise, reducing the number of intra- and postoperative complications [4-16].

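### The primary objective is operating room time, but the primary endpoint times only fixation; total operating time is recorded yet is not an endpoint, and no planned comparison checks the untimed steps

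*Combined protocol and SAP*

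**What the plan says.** The protocol title announces a "Comparison of Operating Room Time Length". In the Objectives table the primary objective is "To compare OR time between conventional treatment techniques (without VSP) vs use of VSP and surgically guided techniques", and the stated justification for the endpoint is "To compare whether or not the intervention (VSP) yielded decrease OR time".

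The endpoint in that same row is ORIF time, and Study Procedures repeats the definition: "ORIF time will be defined as starting after the dissection is complete and fractures are reduced until final screws are placed". Both places add that dissection, reduction and closure should ideally be the same in the two arms.

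The secondary row lists "Age, gender, fracture pattern, Type of archbars, fit guides, type of approach, Surgical revisions, infections, mouth opening" and hardware failure. Total operating time is in neither row. It is, however, a collected item in Study Procedures, and Quality Control & Assurance says that investigators will record it alongside ORIF time.

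The Statistics section has one analysis sentence, a generalized linear model for differences between the two groups. It names no outcome. The power statement (f = 0.4, 25 per group) is not tied to an outcome either.

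**The concern.** The question is about operating room time and the measurement is of one segment of it. A difference in the segment equals a difference in the whole only if everything outside the segment is balanced between arms. The plan hopes for that balance but does not plan to look.

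There is at least one open question about it. According to Study Population, the VSP group uses an intraoperative occlusal splint, and the control group is defined as having none. The text does not say whether placing the splint falls inside the ORIF window.

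At stake is the wording of the main result. The endpoint justification invites a shorter ORIF time to be reported as a decrease in operating room time. The figure that would test that statement is collected but has no endpoint status, so nothing obliges the investigators to report it.

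**Working it through.** **1. Identity.** For each patient, total operating time = ORIF time + time in all other steps. Averaging within arms and subtracting:

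difference in total time = difference in ORIF time + difference in other steps.

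The primary endpoint estimates the first term on the right. The objective asks for the left-hand side. The plan treats the last term as zero and specifies no estimate of it.

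**2. What is inside and outside the window.**
- Probably inside: plate bending. General Information says of the conventional arm, "The reconstruction plate will be bent intra-operatively", whereas the VSP plate is bent beforehand on a model.
- Outside: dissection, reduction, closure.
- Not stated: splint placement (VSP arm only) and arch bar placement.

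**3. The plan's own sample size.** Inputs from Statistics: f = 0.4, power 0.8, significance level 0.05, two groups. With two groups d = 2f = 0.8.
- Normal approximation: 2 × (1.960 + 0.842)² / 0.8² = 24.5, so 25 per group.
- Exact F-test: 25.5, so 26 per group; exact power at 25 per group is 0.791.

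The plan prints both 25 and 26, and both reproduce. This point disputes neither.

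**4. Precision at 25 per arm.** With 48 degrees of freedom, the 95% CI half-width for a difference in means is

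t(0.975, 48) × √(2/25) = 2.0106 × 0.2828 = 0.569 SD of the time analysed.

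**5. Total time against ORIF time (illustration).** The documents give no SD for either time. Let k = SD of total time / SD of ORIF time; every value of k here is an assumption. The half-width for total time is 0.569 × k ORIF SD. For power, assume also that f = 0.4 refers to ORIF time and that the saving in minutes is the same for total time, so d = 0.8/k.

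| k (assumed) | Half-width, ORIF SD | Power at 25 per arm | n per arm for 80% power |
|---|---|---|---|
| 1 (ORIF time itself) | 0.57 | 0.79 | 26 |
| 1.12 | 0.64 | 0.70 | 32 |
| 1.5 | 0.85 | 0.46 | 57 |
| 2 | 1.14 | 0.28 | 100 |
| 3 | 1.71 | 0.15 | 222 |

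**6. Total minus ORIF time.** Its SD also depends on the correlation between ORIF time and the other steps. At k = 1.5 it lies between 1.5 − 1 = 0.5 and 1.5 + 1 = 2.5 ORIF SD, so the half-width lies between 0.569 × 0.5 = 0.28 and 0.569 × 2.5 = 1.42 ORIF SD. If the two are independent, the SD is √(1.5² − 1) = 1.118 and the half-width 0.64. The check can be coarse, and it cannot be planned as a demonstration of equality.

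**The case against.** The best defence is that nothing is hidden. The ORIF definition stands in the same table row as the objective, with the reason for the narrow window, and a window around the step that differs by design is a sensible primary measure. That stands, and it is why ORIF time should remain primary. It does not make ORIF time a measure of operating room time.

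A second defence is that the model sentence may cover all collected data, total operating time included. The sentence does not exclude that reading, but it does not commit to it either. Naming no outcome is a general weakness of the Statistics section.

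Four stronger readings are tempting, and the documents do not support them.
- *ORIF time overstates (or understates) the benefit of VSP.* Nothing shows a time difference outside the window. The Background remark that modelling helps reduction concerns precision, not minutes, and the splint is an unanswered question.
- *Total operating time is undefined.* The supplied text gives no start or stop, but the protocol refers to attached data sheets that were not available and may define it.
- *An ORIF-only report would look more precise about operating room time than the data allow.* That follows only under the assumed SD ratios. At 1.12 the half-widths are 0.64 and 0.57, which is a small gap.
- *The mismatch defeats the cost aim.* Background argues: "Hence, a decreased operating time, anesthesia time, and hospitalization could thereby, potentially, justify the additional preoperative costs". But cost has no endpoint in the Objectives table, and total operating time alone would not answer it. That is a separate gap.

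**Conclusion.** The concern holds and should be fixed. The trial can be valid for fixation time, but as written an ORIF-time result would be read as an operating-room-time result on an assumption that the plan does not commit to check. This conclusion rests on the text and the identity alone, with no numerical assumption.

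The size and direction of any error cannot be stated, because the documents give no step times and no SDs. The only firm figure is the half-width of 0.57 SD of the time analysed at 25 per arm, which assumes a simple comparison of means with all patients evaluable. Every comparison of precision or power between the two times is illustrative.

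**What to change.** - Keep ORIF time as the primary endpoint and describe its result as fixation time.
- Add total operating time to the Objectives table as a secondary endpoint. State its start and stop, or cite the data sheet that does. Say whether splint and arch bar placement fall inside each window.
- In Statistics, name both times as outcomes of the model. Report the between-arm difference in total time in minutes with its 95% CI, whatever the primary result.
- Report total minus ORIF time by arm, with the difference and CI, as a descriptive check. Do not read a non-significant difference as equality.
- Base any statement about operating room time on total operating time.
- If total time is not made an endpoint, restate the primary objective and its justification as fixation time.

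The cost is one table row, one definition or citation, and two further fits on data already due to be collected. There are three downsides. Total time may be more variable, so the aim is an estimate with its interval, not a decisive test. This version is dated 02/10/2021 and the stated study period opens in November 2019; if patients had already been enrolled (not stated), times recorded before the definition is fixed may not match it. And the operating-room-time result may turn out less favourable than the fixation result.
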